## Objectives, Endpoints, and Estimands:

The following objectives and endpoints apply to both intervention-specific appendices (ISAs).

Primary Objective	Endpoints
To demonstrate that tirzepatide at the MTD (10 mg or 15 mg) QW is superior to placebo for mean decrease in AHI.	Change in AHI from baseline to Week 52 (events per hour).
Key Secondary Objectives (controlled for type I error)	Endpoints

To demonstrate that tirzepatide at the MTD (10 mg or 15 mg) QW is superior to placebo for
 
 
• Change in AHI
 
• A hierarchical assessment of PROs
 
• Clinically meaningful change in AHI
 
• Achieving OSA remission or mild nonsymptomatic OSA
 
• Change in body weight
 
• Change in inflammatory status
 
• Change in SBP
 
	
From baseline to Week 52
 
 
• Percent change in AHI
 
• A hierarchical combination of the following: 
 
◦ Change in FOSQ-10 score
 
◦ Change in FOSQ (30 items) Vigilance domain score
 
◦ Change in FOSQ (30 items) Activity Level domain score
 
 
 
• Percent of participants with <math>\geq 50\%</math> AHI reduction
 
• Percent of participants with 
 
◦ AHI <math>< 5</math> or
 
◦ AHI 5-14 with ESS <math>\leq 10</math>
 
 
 
• Percent change in body weight
 
• Change in hsCRP concentration
 
 
From baseline to Week 48a
 
 
• Change in SBP
 

Abbreviations: AHI = Apnea-Hypopnea Index; ESS = Epworth Sleepiness Scale; FOSQ = Functional Outcomes of Sleep Questionnaire; hsCRP = high-sensitivity C reactive protein; MTD = maximum-tolerated dose;

OSA = obstructive sleep apnea; PROs = patient-reported outcomes; SBP = systolic blood pressure; QW = once weekly.

a BP will be assessed at Week 48 because PAP suspension at Week 52 may confound BP assessment.

For estimands guiding statistical analyses, see Section 9.3.1.

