### 3. Objectives, Endpoints, and Estimands

The following objectives and endpoints apply to both ISAs.

Primary Objective	Endpoints
To demonstrate that tirzepatide at the MTD (10 mg or 15 mg) QW is superior to placebo for mean decrease in AHI.	Change in AHI from baseline to Week 52 (events per hour).
Key Secondary Objectives (controlled for type I error)	Endpoints

To demonstrate that tirzepatide at the MTD (10 mg or 15 mg) QW is superior to placebo for
 
 
• Change in AHI
 
• A hierarchical assessment of PROs
 
• Clinically meaningful change in AHI
 
• Achieving OSA remission or mild nonsymptomatic OSA
 
• Change in body weight
 
• Change in inflammatory status
 
• Change in SBP
 
	
From baseline to Week 52
 
 
• Percent change in AHI
 
• A hierarchical combination of the following: 
 
◦ Change in FOSQ-10 score
 
◦ Change in FOSQ (30 items) Vigilance domain score
 
◦ Change in FOSQ (30 items) Activity Level domain score
 
 
 
• Percent of participants with <math>\geq 50\%</math> AHI reduction
 
• Percent of participants with 
 
◦ AHI <math>< 5</math> or
 
◦ AHI 5-14 with ESS <math>\leq 10</math>
 
 
 
• Percent change in body weight
 
• Change in hsCRP concentration
 
 
From baseline to Week 48a
 
 
• Change in SBP
 

Other Secondary Objectives	Endpoints

To demonstrate that tirzepatide at the MTD (10 mg or 15 mg) QW is superior to placebo for
 
 
• Change in excessive daytime sleepiness
 
• Change in patient-reported functional status as assessed by FOSQ (30 items)
 
• Change in body weight
 
	
From baseline to Week 52
 
 
• Change in ESS score
 
• Change in all other FOSQ domain scores
 
• Percent of participants who achieve 
 
◦ <math>\geq 10\%</math> body weight reduction
 
◦ <math>\geq 15\%</math> body weight reduction
 
◦ <math>\geq 20\%</math> body weight reduction
 
 
 

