#### Type of Participant and Disease Characteristics

2. Previously diagnosed moderate-to-severe OSA with an AHI  $\geq 15$ , as diagnosed with PSG, home sleep apnea test (HSAT), or other method that meets local guidelines prior to Visit 1. See Section 10.10 for definitions of apnea and hypopnea.
3. AHI  $\geq 15$  on PSG as part of the trial at Visit 1.
4. In the investigator's opinion, are well-motivated, capable, and willing to
  - learn how to self-inject study intervention, as required for this protocol (visually impaired persons who are not able to perform the injections must have the assistance of a sighted individual trained to inject study intervention; persons with physical limitations who are not able to perform the injections must have the assistance of an individual trained to inject study intervention)
  - inject study intervention (or receive an injection from a trained individual if visually impaired or with physical limitations), and
  - follow study procedures for the duration of the study, including, but not limited to: follow lifestyle advice (for example, dietary restrictions and exercise plan), maintain a study diary, and complete required questionnaires.

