Baseline is defined as the last non missing measurement at or before the randomization visit (Visit 2) unless otherwise specified.

Analysis of covariance will be used to analyze continuous variables collected only at baseline and endpoint. The model will include treatment and strata (pooled country/geographic region, AHI stratum [moderate (AHI  $\geq 15$  and AHI  $< 30$ ), severe (AHI  $\geq 30$ )] and gender) as fixed effects and baseline as a covariate. The ANCOVA model for AHI analysis will include baseline AHI instead of the AHI stratum as a fixed covariate.

The MMRM analysis, a restricted-maximum-likelihood-based model, will be used to analyze continuous longitudinal variables. All the longitudinal observations at each scheduled postbaseline visit will be included in the analysis. The model will include the fixed class effects of treatment, strata (pooled country/geographic region and gender), visit, and treatment-by-visit interaction, as well as the continuous, fixed covariate of baseline value. For analyses of variables other than AHI, the AHI stratum will also be included in the model. Significance tests will be based on least-squares means and Type III tests.

For continuous measures, summary statistics may include sample size, mean, standard deviation, median, minimum, and maximum for both the actual and the change from baseline measurements. Least-square means and standard errors derived from the analysis models will also be displayed for the change from baseline measurements. Treatment comparisons will be displayed showing the treatment difference least-square means and the 95% confidence intervals for the treatment differences, along with the p-values for the treatment comparisons.

For categorical measures, summary statistics may include sample size, frequency, and percentages. Fisher's exact test or Pearson's chi-square test will be used for treatment comparisons unless otherwise specified.

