| | | 
Section 4.1:
 
 Added language on baseline AHI. Modified the postbaseline definition for PRO measures. Updated that geographic region will be used in lieu of pooled country as a covariate in analysis models. Changed AHI groups to be included in the model as covariates. | 
 Language added for clarification. Updated to clarify the definition. Changed to reduce the number of strata in the model and to keep enough participants in each covariate strata. Changed the group category from “moderate” to “not severe” to incorporate inadvertently enrolled participants. |

| SAP Version | Approval Date | Change | Rationale |
|-------------|---------------|---|---|
| | | 
Section 4.1.2:
 
 Updated missing data and imputation method in Table GPIF.4.2. | 
 Missing data imputation algorithm revised, in part to include inadvertent enrollees in analysis, and language on missing data clarified per FDA feedback. |
| | | 
Section 4.1.2:
 
 Added no OSA and mild categories to baseline OSA category | 
 Added to account for inadvertently enrolled patients |
| | | 
Section 4.1.6:
 
 Added definition for baseline and postbaseline concomitant medication use. | 
 Clarified definition for related tables and listings. |
| | | 
Section 4.2:
 
 Added definition for participant study disposition. | 
 Clarified the definition of participant study disposition based on collected CRF data. |
| | | 
Section 4.4.1.2:
 
 Added analysis for change in log hypoxic burden. Added reporting of unconditional risk difference from logistic regression. | 
 Log scale is deemed appropriate for analysis as the measure is an area under the curve. Added to provide additional measure of treatment effect in accordance to FDA guidance. |

| SAP Version | Approval Date | Change | Rationale |
|-------------|---------------|---|--|
| | | Section 4.6: 
 Added hepatobiliary events, malignancies, and abuse potential as special safety topics. | 
 Updated to provide information on special safety topics. |

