1.1. Objectives, Endpoints, and Estimands

| Objective | Endpoints |
|--|--|
| Primary | |
| To demonstrate that tirzepatide at the MTD (10 mg or 15 mg) QW is superior to placebo for decrease in AHI. | Change in AHI from baseline to Week 52. |
| Key Secondary (controlled for Type 1 error) | |
| To demonstrate that tirzepatide at the MTD (10 mg or 15 mg) QW is superior to placebo for | From baseline to Week 52 |
| Percent change in AHI | Percent change in AHI |
| Clinically meaningful change in AHI | Percent of participants with $\geq 50\%$ AHI reduction |
| Achieving OSA remission or mild non-symptomatic OSA | Percent of participants with AHI < 5 or AHI 5-14 with ESS ≤ 10 |
| Change in body weight | Percent change in body weight |
| Change in inflammatory status | Change in hsCRP concentration |
| Hypoxic burden | Change in SASHB (% min/hour) |
| Change in PROs | Change in ^a : PROMIS Sleep-related impairment short form 8a PROMIS Sleep disturbance short form 8b |
| Change in SBP | From baseline to Week 48 ^b Change in SBP |
| Other Secondary | |
| To demonstrate that tirzepatide at the MTD (10 mg or 15 mg) QW is superior to placebo for | From baseline to Week 52 |
| Change in excessive daytime sleepiness | Change in ESS score |
| Change in patient-reported functional status as assessed by FOSQ (30 items) | Change in FOSQ-10 score Change in FOSQ (30 items) Score Change in all FOSQ domain scores, specifically General Productivity Activity level Vigilance Social outcomes Intimate and sexual relationships |
| Change in body weight | Percent of participants who achieve $\geq 10\%$ body weight reduction $\geq 15\%$ body weight reduction $\geq 20\%$ body weight reduction |
| Change in lipid parameters | Change in HDL-cholesterol non-HDL-cholesterol triglycerides |

| Objective | Endpoints |
|---|---|
| A hierarchical assessment of PRO change | A hierarchical combination of the following: Change in PROMIS Sleep-related impairment short form 8a Change in PROMIS Sleep disturbance short form 8b |
| Change in supportive secondary PROs | Change in: SF-36v2 acute form domain and summary scores Percent of participants with improved categorical shift in: PGIS-OSA Sleepiness PGIS-OSA Fatigue PGIS-OSA Snoring Proportion of participants achieving clinically meaningful within-patient change in: PROMIS Sleep-related impairment PROMIS Sleep disturbance |
| Insulin Change in DBP | Change in fasting insulin From baseline to Week 48 ^a Change in DBP |
| Exploratory | |

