4.1.5. Participant Characteristics

A listing of participant demographics for all randomized participants will be provided. The demographic and baseline clinical characteristics will also be summarized by study treatment for all randomized participants. Baseline demographic and clinical characteristics of special interest include but are not limited to:

- age (years)
- sex (female, male)
- race
- ethnicity
- height (cm)
- weight (kg)
- BMI (kg/m²)
- waist circumference (cm)
- age group (<50, ≥50)
- BMI group (<35, ≥35 and <40, ≥40 kg/m²)
- OSA severity (none [AHI <5], mild [AHI ≥5 and AHI <15], moderate [AHI ≥15 and AHI <30], or severe [AHI ≥30])
- geographic region (US/OUS), and
- country.

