4.4.1.1. Main Analytical Approaches

Analysis of percent change in AHI, percent change from baseline to Week 52 in body weight, change from baseline to Week 52 in log of high-sensitivity C-reactive protein, change from baseline to Week 48 in SBP, change from baseline to Week 52 in PROMIS Sleep-related impairment, change from baseline to Week 52 in PROMIS Sleep disturbance, and change from baseline to Week 52 in log of hypoxic burden will be conducted in a manner similar to the primary efficacy analyses using an ANCOVA model with treatment, strata (geographic region [US/OUS], AHI stratum [not severe (AHI <30), severe (AHI \geq 30)], and gender), and baseline of the corresponding variable as a covariate for the treatment regimen estimand. If the hypoxic burden is reported to be 0, log (1) will be used in place of the log of hypoxic burden. The analysis method utilizing data from both ISAs for change from baseline to Week 52 in PROMIS sleep Impairment and PROMIS Sleep disturbance is described in the integrated efficacy analysis plan.

For the efficacy estimand, the MMRM analyses will be conducted as described in Section 4.1. For both estimands, analysis of percent change in AHI will adjust for the continuous, fixed baseline value of AHI instead of the baseline AHI stratum (not severe, severe).

Comparisons at the 52-week visit between the treatments relative to the proportion of participants achieving \geq 50% AHI reduction and AHI <5 or (AHI 5 through 14 and ESS \leq 10) will be conducted using logistic regression analysis including the following terms as a covariate:

- treatment
- geographic region (US/OUS)
- baseline AHI, and
- gender.

Unconditional risk differences will also be provided for these endpoints using logistic regression (Ye et al. 2023).

Analysis aligned to each estimand will be evaluated at the full significance level of 0.05 contingent on reaching statistical significance of the primary objective.

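### The remission-or-mild responder endpoint stops its mild band at AHI 14, while the trial's only definition of mild OSA runs up to, but excludes, 15; a fractional AHI between them counts as non-response (minor effect)

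*SAP*

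**What the plan says.** The endpoint is a key secondary endpoint under Type 1 error control, with the objective label "Achieving OSA remission or mild non-symptomatic OSA" (SAP 1.1). Its mild band is stated six times, and every statement stops at 14:

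- Protocol 1.1 and 3, and SAP 1.1: "AHI 5-14 with ESS" of 10 or less.
- SAP 4.4.1 and 4.4.1.1: "AHI 5 through 14 and ESS" of 10 or less.
- Protocol 9.3.3: the same band as inequalities, with AHI at least 5 and at most 14.

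The severity classes are stated elsewhere:

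- SAP 4.1.5 lists "OSA severity (none [AHI <5], mild [AHI" from 5 to below 15], then moderate from 15 to below 30, then severe from 30. This is a baseline table. The SAP version history records "Added no OSA and mild categories to baseline OSA category", to account for inadvertently enrolled patients.
- Protocol 9.3.1 gives the "AHI stratum [moderate (AHI" at least 15 and below 30)].
- Protocol 5.1 requires "Previously diagnosed moderate-to-severe OSA with an AHI" of at least 15.

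On measurement, the primary endpoint is "Change in AHI from baseline to Week 52 (events per hour"), and Protocol 8.1.1.1 bases all AHI endpoints on the central PSG reading. Neither document gives decimal places, rounding or truncation for AHI. SAP 4.1.2 prescribes multiple imputation for the treatment regimen estimand. It does not say whether AHI itself or responder status is imputed, or whether imputed values are rounded.

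**The concern.** The endpoint is named for mild disease but is cut one unit short of where the trial says mild disease ends. Everywhere else the AHI classes meet without a gap: below 5 and from 5, below 15 and from 15, below 30 and from 30. Only the top of this band leaves an interval, above 14 and below 15, that is neither a response nor moderate OSA.

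At stake is a small, avoidable misclassification in a confirmatory responder endpoint, and a reported *mild* category narrower than the mild category in the baseline table. The same responder rule feeds the ISA2 sensitivity analysis in SAP 4.4.1.2 and the unconditional risk differences in SAP 4.4.1.1.

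**Working it through.** **1. Can a value fall in the gap?** AHI is events divided by hours. The hours of scored time below are assumed.

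| Hours | Event counts giving 14 < AHI < 15 |
|---|---|
| 6 | 85 to 89 |
| 7 | 99 to 104 (AHI 14.1 to 14.9) |
| 8 | 113 to 119 |

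If the central reading keeps fractions, these values occur. If it rounds to whole numbers or truncates, every reported value is either 14 or less or 15 or more, and the two cuts select the same observed participants. Imputed AHI could still be fractional if AHI itself is what is imputed.

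**2. Is there a figure in the plan to reproduce?** No. Neither document gives a responder rate, power or AHI distribution for this endpoint, so the size has to be illustrated.

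**3. Inputs.**

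- From SAP 5 and Protocol 9.5: 103 per arm; 50% improvement in percent change in AHI; SD 50%; dropout 25%, which leaves 103 × 0.75 ≈ 77 per arm.
- From Protocol 5.1: baseline AHI at least 15.
- Assumed: baseline AHI lognormal, geometric mean 30, 40 or 50, log-SD 0.4, 0.6 or 0.8, truncated at 15. Percent change is normal, with placebo mean 0 or −10 and treated mean 50 points lower; changes below −100% count as AHI 0. The share *e* with ESS of 10 or less is 0.5 or 0.8, equal in both arms and independent of AHI.
- This gives 3 × 3 × 2 × 2 = 36 scenarios.

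**4. Formula.** With F the Week 52 AHI distribution and cut c = 14 or 15, the responder probability is p = F(5) + e × (F(c) − F(5)). The number reclassified per arm is n × e × (F(15) − F(14)).

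**5. One scenario in full** (geometric mean 40, log-SD 0.6, placebo mean 0, e = 0.8).

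| | F(5) | F(14) | F(15) | p, cut at 14 | p, below 15 |
|---|---|---|---|---|---|
| Tirzepatide | 23.4% | 40.6% | 42.5% | 37.1% | 38.7% |
| Placebo | 4.3% | 12.2% | 13.5% | 10.6% | 11.6% |

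For example, treated p with the cut at 14 is 23.4 + 0.8 × (40.6 − 23.4) ≈ 37.1 (unrounded inputs). The risk difference goes from 26.5 to 27.1 points, and the odds ratio from 4.97 to 4.80. Power at 77 per arm goes from 97.7% to 97.8%.

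**6. All 36 scenarios.**

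| Quantity | Tirzepatide | Placebo |
|---|---|---|
| Share with 14 < AHI < 15 | 1.60 to 2.56% | 0.78 to 2.08% |
| Reclassified per 103 | 0.82 to 2.11 | 0.40 to 1.72 |
| Reclassified per 77 | 0.61 to 1.57 | 0.30 to 1.28 |

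Moving from the cut at 14 to below 15:

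- raises the risk difference by 0.15 to 0.68 points;
- lowers the odds ratio in 36 of 36 scenarios;
- changes power by −0.03 to +0.06 points at 103 per arm and by −0.12 to +0.23 points at 77 per arm.

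Power is for an unadjusted two-proportion test, not the planned adjusted logistic regression.

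**The case against.** The strongest reply is that nothing is broken. All six statements agree, and the inequalities in Protocol 9.3.3 return one answer for any AHI, whole or fractional. An endpoint is defined by its cut and not by its label. The benchmark is a baseline table whose mild class was added to describe inadvertent enrollees, and no passage ties the Week 52 endpoint to it. The wording with *through* reads naturally as whole-number banding, and AHI precision is simply not visible in the documents.

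Much of this stands. The rule is internally consistent and programmable, the SAP 4.1.5 classes are for baseline, and silence on decimals does not show that fractions are kept. But SAP 4.1.5 is the only meaning of mild that the trial states, and moderate starting at 15 is stated independently in Protocol 9.3.1. Neither document gives a reason for stopping at 14. If AHI is in whole numbers or truncated, writing below 15 gives the same observed responders.

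The equal ESS share in both arms is also open to challenge, because the trial hopes to show an ESS difference. With a share of 0.8 on tirzepatide and 0.5 on placebo, a crude upper limit for the shift in risk difference is 0.8 × 2.56 − 0.5 × 0.78 ≈ 1.7 points, which is still small.

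A reader might infer more than the documents support:

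- *The protocol and SAP conflict on the endpoint.* They do not; the mismatch is between the cut and the label.
- *Participants will certainly be misclassified.* This depends on AHI precision, which is not stated.
- *The comparison is biased or the error rate inflated.* The same rule applies in both arms and is fixed in advance.
- *A Week 52 severity table will contradict the endpoint.* None is planned; the severity classes are specified only at baseline.

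**Conclusion.** The point holds as a minor one. The mild band of this endpoint ends at 14, while the trial's own mild class ends just below 15. Any AHI strictly between the two, observed or imputed, with ESS of 10 or less counts as non-response under an endpoint named for mild non-symptomatic disease.

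Under the planning values this concerns roughly one or two treated participants and at most about two placebo participants per 103, and lowers the risk difference by less than 0.7 points. The direction depends on the scale: the present cut gives a slightly smaller risk difference and a slightly larger odds ratio. The sizes rest on assumed baseline AHI and ESS distributions that the documents do not supply, and the effect is zero for observed values if the central AHI is whole-number or truncated.

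**What to change.** Before the first ISA is unblinded, define the endpoint as AHI < 5, or (AHI ≥ 5 and AHI < 15 with ESS ≤ 10), applied to the AHI as centrally reported or as imputed, without further rounding.

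- Make the change in SAP 1.1, 4.4.1 and 4.4.1.1. SAP 4.4.1.2 refers back to 4.4.1.1 and needs no separate edit.
- Align Protocol 1.1, 3 and 9.3.3. Alternatively, record the change and its justification in the SAP, which Protocol 9.3.1 allows when no principal feature of the master protocol is altered.

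The cost is a text edit in six sections across two documents and one line in the derivation specification, with no effect on data collection or enrolment. If the sponsor regards the bound as a principal feature, a protocol amendment is needed, and Protocol 10.1.1 requires IRB/IEC approval before it is implemented.
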